3.6 Randomization Protocol

Following enrollment and completion of the initial length assessment, patients will be categorized into the appropriate strata based on their baseline stretched penile length; strata categorized as <10 cm, 10cm-13cm, 13.1cm-16cm, >16cm stretched length. Each stratum will have a separate randomization table provided such that one of three possible outcomes will occur no less frequently than every other case. This is done to better account for baseline variables that may impact outcomes and to assist with matching groupings appropriately.

The explanation of which grouping the patient is assigned will then be reviewed, and if the patient subject is assigned to the treatment group, a RestoreX® device will be provided.

4 Study Procedures

4.1 Pre-Operative Assessments

- Captured as a function of standard care
 - EPIC-50
 - IIEF-15
 - Disease specific variables
 - Demographics
- Participant consented

4.2 Baseline Assessment

- Participant consented (if they were not originally consented at the pre-operative appointment)
- Obtained prior to randomization at time of catheter removal (part of standard care)

- Objective assessments
 - Penile length – measured from pubic symphysis to glanular corona
- Subjective questionnaires (attached)
 - Disease specific history
 - IIEF-15 (for patients who have not completed pre-operatively)
- Device usage diary provided for treatment group

4.3 6 Month Visit

- Penile length assessment
- Questionnaires (attached)
 - 6 month
 - IIEF-15
- Device usage diary retrieved from treatment group
- Device usage diary given to all participants (enter open label phase)

4.4 9 Month Visit

- Penile length assessment
- Questionnaire
 - 9 month
 - IIEF-15
- Retrieve device usage diary

4.5 Assessment of Length

Penile length measurements will be obtained by a member of the clinical team using a measurement from the pubic symphysis to the corona of the glans penis. Measurements will be obtained post-operatively (after catheter removal) and at the 6 and 9 month follow-ups.

See **Attachments – Device Usage Diary, Disease Specific History, IIEF-15, Questionnaire 6 Month and 9 Month**

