7.3 RECORDS RETENTION17

8 STUDY FINANCES 18

8.1 FUNDING SOURCE 18
8.2 CONFLICT OF INTEREST 18
8.3 SUBJECT STIPENDS OR PAYMENTS 18
8.4 REGULATORY INFORMATION 18
9 REFERENCES 19

LIST OF ABBREVIATIONS

AE	Adverse Event/Adverse Experience
HIPAA	Health Insurance Portability and Accountability Act
PTT	Penile traction therapy
PD	Peyronie's Disease
RCT	Randomized controlled trial

Study Summary

Title	Penile Lengthening Maintenance Post-prostatectomy
IRB Protocol Number	18-001013
Methodology	Controlled randomized study
Overall Study Duration	3 years
Subject Participation Duration	9 months
Objectives	Evaluate the efficacy of the RestoreX penile traction device in preventing loss of penile length in men undergoing prostatectomy
Number of Subjects	90
Diagnosis and Main Inclusion Criteria	Men undergoing prostatectomy
Study Device	RestoreX®, penile traction therapy
Duration of Exposure	Subjects will use device for 5 months for: 30 minutes, once daily, 5 days a week OR 30 minutes, twice daily, 7 days a week After the randomized period, all subjects will be entered into an open-label phase where they may choose to use or not use the device for 3 additional months
Reference therapy	During the randomized phase, the use of the device will be compared against a control group using no traction therapy In the open label phase, results at the end of 9 months will be compared to those from baseline and at the beginning of the open label phase
Statistical Methodology	Stratification of subjects prior to randomization to assure an equal representation based on baseline penile length. Statistical comparisons will be made comparing total penile length prior to and following therapy. Comparisons of subjective questionnaire responses will also be made between groups and at the various time points captured.

1 Introduction

This document is a protocol for a human research device study. This study will be carried out in accordance with the procedures described in this protocol, applicable United States government regulations and Mayo Clinic policies and procedures.

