2.1 Primary Objective

1. The primary objective is to assess penile length pre and post completion of RestoreX® traction therapy compared to control groups (no treatment) of subjects who have undergone a prostatectomy.

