3.5 Study Schema

Prior to surgery, data will be recorded by the surgeon using the current standard of care questionnaires (EPIC-50, IIEF-15 disease specific variables, and demographics).

Following surgery, patients will be seen in the clinic based on the standard routine clinical practice for their catheter removal (approximately 1-3 weeks post-prostatectomy). At this time, and after the patient has consented, they will undergo initial study penile length assessments (described later in the protocol) and be educated on how to use the device properly by a trained nurse. Patients will then be given a baseline questionnaire to complete. In some cases, patients may not have been provided the IIEF-15 questionnaire prior to surgery. For these patients that have not yet filled out this questionnaire and had their data recorded in their records, they will instead receive the IIEF-15 questionnaire during this baseline visit.

Once consent and study assessments are completed, the patients will be randomized into one of three groups:

1. PTT for 30 min 1x/day, 5 days/week
2. PTT for 30 min 2x/day, 7 days/week
3. Control (no treatment)

Patients in the treatment arm will record a daily journal of their usage of the device. Patients will then begin using the device 4 weeks after surgery as instructed for the times appropriate to their group. This ensures adequate time for the patient to recover from their procedure before beginning to use the device. The study coordinator will call the patient to remind them to begin using the device.

After 5 months of using the device (+1.5 months permitted), patients will return for subsequent assessments (see below) and a follow-up questionnaire. At this time, patients will be encouraged to report any adverse events. They will also be requested to bring their device back to the clinic to review proper usage and any questions on the device. After completion of the subsequent assessments, patients will begin a 3-month, open-label phase of the trial. During this period, the patients will be allowed to use the device for 30 minutes at a time, with a frequency to be determined by the patient.

After completion of the 3-month open-phase portion of the trial, patients will return to the clinic to undergo final assessments, which are identical to the 6-month assessments. Patients will then be encouraged to self-report any additional adverse events (AE's) that they encounter over the subsequent 6 months.

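### Nothing in the plan keeps the person who measures penile length at 6 months unaware of the arm, at a visit where only traction men should have a trial-issued device to bring and a diary to return.

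*Combined protocol and SAP*

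**What the plan says.** Section 2.1 makes length the primary outcome: "The primary objective is to assess penile length pre and post completion of" traction, compared with untreated controls. The Study Summary, under Reference therapy, describes the randomised contrast: "During the randomized phase, the use of the device will be compared against a control group using no traction therapy". There is no sham device.

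On who measures, section 4.5 says only "Penile length measurements will be obtained by a member of the clinical team", and then gives the anatomical landmarks and the visits.

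The sections that bear on what a measurer could see or know are these:

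- **Baseline (3.5, 4.2).** Length is measured at catheter removal, before randomisation.
- **Allocation (3.6).** The assignment is reviewed with the patient, and "if the patient subject is assigned to the treatment group, a RestoreX® device will be provided".
- **Start of use (3.5).** Men in the treatment arm keep a daily journal. The study coordinator telephones to remind the patient to begin using the device.
- **6-month visit (3.5).** "They will also be requested to bring their device back to the clinic to review proper usage and any questions on the device".
- **6-month visit (4.3).** The list includes the length assessment, the questionnaires, and "Device usage diary retrieved from treatment group". All men are then given a diary for the open-label phase.

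**The concern.** A no-treatment comparison cannot be masked from the patient, but it can be masked from the person holding the ruler. The plan does not attempt this. The visit that supplies the randomised primary comparison is also the one at which a device on the table or a diary in the hand would identify a traction patient. A clinical-team member may also know the arm already from reviewing the assignment, handing out the device or making the reminder call.

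A measurer who knows the arm may read one group slightly longer or shorter without intending to. An error of that kind looks the same as a treatment effect.

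**Working it through.** **1. Is there a masking provision?** The protocol has no statement that masks the measurer, separates that person from staff who handle devices or diaries, or sets the measurement ahead of the device review. Section 5.1 lets the patient or the provider record data and names no masked recorder. Section 4.3 lists length first, but a bullet list is not a stated sequence. The attachments are not part of the text reviewed, so the absence is established for the protocol text only.

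**2. Do device and diary separate the arms at 6 months?** Some wording is general. Section 3.3 says participants would be given a device, 3.5 asks patients to bring theirs, and Table 1 shows a diary at baseline without naming an arm. The specific sections settle it. Section 3.6 ties the device to assignment to treatment, 4.2 gives the baseline diary to the treatment group, and 4.3 collects it from that group. Read together, only traction men should have a trial-issued device and a diary to return at this visit. Section 8.4 says the device is on public sale, so a control could own one, but not from the trial.

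**3. Does the error cancel?** Let e_T and e_C be the mean measurement errors at 6 months in the traction and control arms. Baseline precedes randomisation, so its error has no expected difference between arms. Then:

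expected observed difference = true difference + (e_T − e_C)

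This holds for 6-month length and for change from baseline. If a fraction f of traction men are shifted by d, and no controls are, the bias is f × d. More patients do not reduce it.

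**4. Illustrative size.** The plan gives no SD, alpha, test or measurement error, so there is no figure of its own to reproduce. From section 3.4: 30 men per arm, hence 60 traction v 30 control when the two regimens are pooled. Assumed: no true effect, a two-sided 5% test on centimetres, an SD of the analysed length outcome of 1.0 to 2.0 cm, all 90 men measured, and every traction reading shifted by d = 0.25 cm.

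SE = SD × √(1/n₁ + 1/n₂); rate = P(|Z + d/SE| > 1.96)

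| SD (cm) | SE, 60 v 30 | d/SE | False-positive rate |
|---|---|---|---|
| 1.0 | 0.224 | 1.12 | 0.201 |
| 1.5 | 0.335 | 0.75 | 0.116 |
| 2.0 | 0.447 | 0.56 | 0.086 |

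One regimen against control (30 v 30) gives 0.162, 0.099 and 0.077 for the same SDs.

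The result depends heavily on d. For 60 v 30 and SD 1.0 to 2.0 cm, a mean shift of 0.125 cm (half the traction men shifted by 0.25 cm) gives about 9% to 6%. A shift of 0.5 cm gives about 61% to 20%. With no shift the rate stays at 5%.

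Section 3.5 lets men who cannot travel return only questionnaires and diary, so fewer lengths may be measured. With 40 v 20 and a 0.25 cm shift, the rate is about 15% to 7%. The bias in the estimate is still 0.25 cm.

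**The case against.** The best defence is that the plan never claims to be blinded, the men must know their arm, and 4.3 already puts length at the top of the visit list. Nothing says the measurer sees the device or diary. This stands as far as it goes: the text shows an open route to unmasking, not that unmasking will happen. It does not excuse the gap, because the measurer can be masked even where the patient cannot.

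The illustration can also be attacked. The shift and the SD are assumed, and section 5.2 says data will be normalised to pre-operative length, so a plain centimetre comparison may not be the planned analysis. That is fair. The figures show only how a given error would act, and 0.25 cm is neither an estimate nor an upper limit.

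A reader might also infer more than the text supports:

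- **That the nurse who teaches device use thereby learns the arm.** Section 3.5 describes the teaching before randomisation and does not limit it to traction men. The roles that carry knowledge of the arm are those that review the assignment, hand out the device, make the reminder call or handle the diary.
- **That the problem has gone by 9 months because all men are then in the open-label phase.** All men have a diary by then, but no section states that controls are issued a device at 6 months. Open-label use is optional, and the same person may measure at both visits.
- **That the inventor's role disclosed in 8.2 points to biased readings.** The section reports an institutional review and says nothing about who measures.
- **That the reading depends on how hard the assessor pulls.** The strata in 3.6 use stretched length, but 4.5 does not say whether follow-up length is stretched. That is a separate question of standardisation, and this point does not rest on it.

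**Conclusion.** The point holds as an unprotected risk to the primary comparison. The measurer is unspecified, the order of the visit is not fixed, and device and diary can reveal the arm at 6 months. Because baseline is protected, whatever error knowledge of the arm causes goes undiluted into the randomised difference.

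The size and direction of that error are unknown. The range of about 9% to 20% rests wholly on the assumed 0.25 cm shift in all traction readings, SD of 1.0 to 2.0 cm and two-sided 5% test for 60 v 30. Larger shifts or smaller SDs give more, and smaller shifts give less. A reader might conclude that the trial's error rate is 20%, or that the result will favour traction. The document supports neither. This should be corrected, mainly because prevention is cheap and the error cannot be removed afterwards.

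**What to change.** In 4.3 and 4.5, state that at the 6-month visit:

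1. Length is measured and recorded before any questionnaire, adverse-event, diary or device review.
2. Device and diary are kept out of the measurer's sight, and the patient is asked not to disclose use.
3. Where possible, the measurer is an existing clinical-team member who is not told the arm and who did not review the assignment, hand out the device, make the start-of-use call or handle the diary.

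Apply the same procedure at 9 months, since the arms are not shown to be indistinguishable by then.

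The cost is protocol wording and minor scheduling effort, with no extra visit or test. Masking will be imperfect if a patient discloses his arm. The document does not describe staffing. If no second team member is free, the measure-first order and the concealment still apply, with weaker protection.

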4.6 Schedule of Events

Table 1: Schedule of Events

Study Activity	Pre-operative	Baseline Assessment	6 Month	9Month
----------------	---------------	---------------------	---------	--------

		(post-operative up to 1 mo)		
Consent	X	X		
EPIC-50	X			
IIEF-15	X	X	X	X
Disease Specific History		X		
Length Assessment		X	X	X
Patient Diary Provided		X	X	
Questionnaire 6 Month			X	
Questionnaire 9Month				X

5 Statistical Plan

5.1 Data Handling

All data will be recorded either by the patient themselves or by the provider directly onto printed forms (Attachments). Information will remain de-identified throughout the remainder of the study period and will remain on password protected, Mayo servers.

After completion of the study, de-identified information will be shared with individuals associated with PathRight Medical, Inc. who may assist with portions of the data analysis and/or manuscript drafting. No identifiable information will be sent.

5.2 Statistical Analysis

Analyses will be performed using comparisons within patients of same baseline penile stretch length and between groupings of varying lengths. Comparison of penile length between traction and no traction will be made, as well as reviewing historical records to increase statistical power. Comparison of length from baseline to post-traction for individual participants will also be reviewed.

The data will also be analyzed in three ways: 1- with all patients included, regardless of their compliance to utilize the device for the recommended treatment time, 2- with patients excluded if they failed to achieve 90% compliance with the recommended duration of treatment, 3- with patients excluded if they failed to achieve 80% compliance with the recommended duration of treatment.

Comparisons will also be made on other subjective and objective variables obtained including number of adverse events, complications, subjective responses to questionnaires, or

other information. All data will be normalized based on pre-operative stretched penile length.

6 Safety and Adverse Events

Definition of Adverse Event

Unanticipated Problems Involving Risk to Subjects or Others (UPIRTSO) - any unanticipated problem or adverse event that meets the following three criteria:

Serious: Serious problems or events that results in significant harm, (which may be physical, psychological, financial, social, economic, or legal) or increased risk for the subject or others (including individuals who are not research subjects). These include: (1) death; (2) life threatening adverse experience; (3) hospitalization - inpatient, new, or prolonged; (4) disability/incapacity - persistent or significant; (5) breach of confidentiality and (6) other problems, events, or new information (i.e. publications, interim findings, product labeling change) that in the opinion of the local investigator may adversely affect the rights, safety, or welfare of the subjects or others, or substantially compromise the research data, AND

Unanticipated: (i.e. unexpected) problems or events are those that are not already described as potential risks in the protocol, consent document, not listed in the Investigator's Brochure, or not part of an underlying disease. A problem or event is "unanticipated" when it was unforeseeable at the time of its occurrence. A problem or event is "unanticipated" when it occurs at an increased frequency or at an increased severity than expected, AND

Related: A problem or event is "related" if it is possibly related to the research procedures.

Adverse Event - an untoward or undesirable experience associated with the use of a medical product (i.e. drug, device, biologic) in a patient or research subject.

Serious Adverse Event - adverse events are classified as serious or non-serious. Serious problems/events can be well defined and include:

- Death
- Life threatening adverse experience
- Hospitalization
- Inpatient, new, or prolonged; disability/incapacity
- And/or per protocol may be problems/events that in the opinion of the sponsor-investigator may have adversely affected the rights, safety, or welfare of the subjects or others, or substantially compromised the research data.

All AEs that do not meet any of the criteria for serious, should be regarded as non-serious AEs.

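### Comparing length change across baseline-length groups cut on the same baseline reading can make shorter men appear to do better than longer men, even if traction has no effect

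*Combined protocol and SAP*

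**What the plan says.** Section 3.6 forms the groups: "patients will be categorized into the appropriate strata based on their baseline stretched penile length", with "strata categorized as <10 cm, 10cm-13cm, 13.1cm-16cm, >16cm stretched length". Section 4.5 fixes when length is read: "Measurements will be obtained post-operatively (after catheter removal) and at the 6 and 9 month follow-ups". Neither that section nor the Schedule of Events (4.6) includes a separate screening reading, so the stratum and the baseline value come from the same visit.

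Section 5.2 then plans "comparisons within patients of same baseline penile stretch length and between groupings of varying lengths", and adds: "Comparison of length from baseline to post-traction for individual participants will also be reviewed". The Study Summary, under Statistical Methodology, describes the general approach as before versus after: "Statistical comparisons will be made comparing total penile length prior to and following therapy". Section 5.2 also plans a traction versus no-traction comparison. It names no model, no baseline adjustment and no interaction term, and it does not say whether the comparison "between groupings of varying lengths" is made across the randomised arms.

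On measurement, section 4.5 says "Penile length measurements will be obtained by a member of the clinical team". No replicate readings, fixed assessor or reliability figure is given.

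**The concern.** Length groups are not randomised. When they are cut on a reading that contains error, the short group collects men whose reading was low by chance and the long group collects men whose reading was high by chance. At the next visit the chance part does not repeat. Subtracting the same reading therefore pushes change up in the short group and down in the long group, relative to the average. This is regression to the mean. It needs no device effect and acts in every arm.

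The risk is a subgroup conclusion that traction works best, or protects best, in shorter men when the data contain only this artefact. The same mechanism affects individual baseline-to-follow-up changes when they are read without a control distribution beside them.

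**Working it through.** **Inputs from the documents.** Cut points 10, 13 and 16 cm (3.6); one baseline reading (4.5, 4.6); 30 men per arm in three arms, so 60 traction and 30 control men (3.4, 3.5). The plan has no figure of its own to reproduce on this point.

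**Assumed, because the documents give none.** True length with mean 13 cm and SD 2 cm; independent error of SD e = 0.5, 0.75 or 1.0 cm at each visit; no traction effect; two-sided 5% test.

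**Step 1: spurious change by stratum.** Reliability is r = 4 / (4 + e²), and

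expected change in a stratum = average change − (1 − r) × (stratum mean reading − 13).

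The observed SD is s = √(4 + e²). The mean reading in the <10 cm stratum lies below 13 by s × φ(3/s) / Φ(−3/s), where φ and Φ are the standard normal density and distribution function. The >16 cm stratum mirrors it.

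| e (cm) | 0.5 | 0.75 | 1.0 |
|---|---|---|---|
| s (cm) | 2.062 | 2.136 | 2.236 |
| 1 − r | 0.0588 | 0.1233 | 0.2000 |
| Distance of <10 cm mean from 13 (cm) | 3.92 | 3.97 | 4.04 |
| Shift in each end stratum (product, cm) | 0.23 | 0.49 | 0.81 |
| Gap between end strata (cm, before rounding the shift) | 0.46 | 0.98 | 1.61 |

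Simulation of 1,000,000 men gives gaps of 0.46 / 0.97 / 1.61 cm. The average change is a common constant and cancels in the gap.

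**Step 2: false-positive rate of a two-group test.** Split 60 traction men at 13 cm. Each half has a mean reading s × √(2/π) from 13, so the spurious gap is 2(1 − r) × s × 0.798. If every man has the same true change, change has SD about e√2, and the standard error with 30 against 30 is e√2 × √(2/30).

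| e (cm) | 0.5 | 0.75 | 1.0 |
|---|---|---|---|
| Spurious gap (cm) | 0.194 | 0.420 | 0.714 |
| Standard error (cm) | 0.183 | 0.274 | 0.365 |
| Gap / standard error | 1.06 | 1.53 | 1.96 |
| Rejection, normal approximation | 17% | 32% | 48% |
| Rejection, simulation | 18% | 33% | 50% |

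**Step 3: let true change differ between men.** If true change has SD 1.5 cm, unrelated to length, the SD of change becomes √(2e² + 2.25) and the ratios fall to 0.45 / 0.89 / 1.34. Simulated rejection is about 7 / 14 / 27%. With SD 1.0 cm it is 10 / 20 / 36%.

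**Step 4: contrasts that use the control arm.** The difference between traction and control in the low-minus-high contrast rejects 4.4 / 4.7 / 5.3% (8,000 trials, same true change in all men).

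**Step 5: all 90 men and all four strata.** A second set of assumptions (observed mean 13 cm and SD 2.5 cm, reliability 0.95 / 0.9 / 0.8 / 0.7, no true change, 3,000 runs each) gives 19 / 34 / 66 / 86% false positives for an F test of change across strata. The arm-by-stratum interaction rejects 5.0 / 4.5 / 4.4 / 4.9%, and the traction versus control test 5.1 / 4.1 / 3.3 / 3.2%.

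**The case against.** The strongest reply is that the offending analysis is inferred. The sentence in 5.2 names neither change as the outcome nor traction men alone, and it could mean comparing traction with control within strata and then across them, which is close to the interaction proposed below. That stands as far as it goes: the text is ambiguous. But comparing raw follow-up length across strata would tell little, since the strata differ in length by construction, and the before-versus-after description in the Study Summary makes change a natural reading. Nothing in the plan excludes it.

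A reader might infer that short men will be seen to gain and long men to lose. The documents do not support that. The study's premise is loss of length after prostatectomy, and with an assumed average loss of 1 cm the Step 1 inputs give −0.77 / −0.51 / −0.19 cm in the shortest stratum and −1.23 / −1.49 / −1.81 cm in the longest. Short men simply appear to lose less. Only the relative statement holds.

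The size is also conditional. With error-free measurement the artefact vanishes, and the higher rejection rates assume identical true change in every man. The end strata would hold only about 4 to 5 of 60 traction men each (7 to 9%), so their gap would be poorly estimated. The two-way split and the restriction to traction men are choices made for illustration; Step 5 shows that inflation does not depend on them.

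Finally, 5.2 says that all data will be normalised to pre-operative length. A separate pre-operative reading used as the reference would weaken the link between grouping and subtraction, but neither 4.5 nor 4.6 schedules one.

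**Conclusion.** The point holds in relative and conditional form, as a defect in a secondary analysis. If change is compared across the baseline-length groups, shorter men are favoured over longer men in expectation, with no traction effect and whatever the average change. Under the stated assumptions the end-stratum gap is about 0.5 to 1.6 cm. The false-positive rate of the two-group test is about 18 to 50% with identical true change and about 7 to 27% when true change varies with SD 1.5 cm. Every one of these figures rests on an assumed mean, SD and measurement error.

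Two stronger readings should not be drawn. The primary objective is not compromised: regression to the mean acts equally in all arms within a stratum, and the arm comparison shows no inflation. Nor does the plan contain a responder definition or a responder claim; individual changes are only to be reviewed.

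**What to change.** In 5.2, replace the clause on comparisons "between groupings of varying lengths" with one analysis labelled exploratory: the treatment-by-baseline-length interaction across the randomised arms, in a model of follow-up length adjusted for baseline length. State in advance whether the two traction arms are pooled for this test. If the sponsor meant a comparison of arms within and across strata, this wording says so explicitly. Present individual changes from baseline alongside the control arm's changes, so that the spread expected without traction is visible.

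The cost is one model term and a few lines of text, with no change to visits, measurements or sample size. The downside is low power: with 90 men the interaction test will rarely support a subgroup claim.

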3.4 Consent and Enrollment

Patients attending a penile rehabilitation clinic (either prior to or following surgery) will receive a description of the study. Those interested in participating, will be given the opportunity to meet with the study coordinator to further review study details and formal consent.

Patients that would like additional time to consider their participation will be given another opportunity to meet with the study coordinator up to one month following the prostatectomy.

If the patient expresses interest in participating at any of these times, a formal consent will be reviewed (see **Attachment – Consent Form**).

At enrollment, all participants will be assigned a study identifier, with a master list maintained in a password protected database (Mayo server) linking the patient to the identifier. A total of 30 patients will be enrolled into each arm of the study, for a total of 90 patients enrolled overall. It is estimated that 100 patients will need to be screened to enroll the 90 patients.

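### Section 5.2 brings unspecified historical records into the traction versus no-traction length comparison, and nothing makes the randomised-only comparison primary

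*Combined protocol and SAP*

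**What the plan says.** Section 5.2 (Statistical Analysis) states: "Comparison of penile length between traction and no traction will be made, as well as reviewing historical records to increase statistical power". This is the only mention of historical records in the document. It gives a purpose, but no source, number, period, eligibility, measurement method or way of combining.

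The comparison is the primary one by way of section 2.1, where length after traction is "compared to control groups (no treatment) of subjects who have undergone a prostatectomy". The Study Summary (reference therapy) says that in the randomised phase "the use of the device will be compared against a control group using no traction therapy". Under 3.5, "the patients will be randomized into one of three groups", one of them untreated, and 3.4 adds: "A total of 30 patients will be enrolled into each arm of the study, for a total of 90 patients enrolled overall".

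Section 5.2 also says: "All data will be normalized based on pre-operative stretched penile length". Section 3.6, by contrast, uses the enrolment measurement: "patients will be categorized into the appropriate strata based on their baseline stretched penile length".

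**The concern.** A purely descriptive look at old records cannot raise power, so the stated purpose implies that they enter the inference somehow. Two readings are open.

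- **External patients.** Untreated men from the past are added to the control side. Non-randomised men then enter the primary contrast, and any difference from the concurrent controls in era, measurement or selection becomes bias. It can run either way, creating a benefit or hiding one. With source and method unstated, both could be chosen after results are seen.
- **Participants' own charts.** The records supply a covariate, for instance a pre-operative length. There is then no such bias. The defect is an unnamed variable and an unsettled baseline.

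The baseline problem also stands on its own, because 5.2 normalises to a length that no visit is scheduled to collect.

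**Working it through.** **Does another section settle the meaning?**

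- Section 2.1 refers to untreated control groups without limiting them to randomised men.
- The Study Summary names a no-traction reference group for the randomised phase. It neither calls that contrast primary nor excludes other data.
- The three analysis sets in 5.2 differ only by compliance, and none is named primary.
- Section 5.1 has all data entered on printed forms by patient or provider. It describes no extraction of past records under either reading.

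**Is a pre-operative length collected?** Section 3.5 says: "Prior to surgery, data will be recorded by the surgeon using the current standard of care questionnaires". It and 4.1 list EPIC-50, IIEF-15, disease-specific variables and demographics, with no length. Section 4.5 and Table 1 place length after catheter removal and at 6 and 9 months. So strata use a post-operative length and normalisation uses an unscheduled pre-operative one.

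**Size if external patients were pooled.** The plan gives no figure to reproduce.

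- *From the documents:* 30 per arm, two traction arms, one control arm (3.4, 3.5).
- *Assumed:* H past patients, a mean shift of b SD, simple unadjusted pooling, equal SDs, two-sided 5%, no dropout, and the layout. The plan does not say whether the traction arms are combined, so both layouts are shown.

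Bias = b × H/(30 + H). SE = √(1/n_T + 1/(30 + H)). Type I error ≈ Φ(−1.96 + bias/SE) + Φ(−1.96 − bias/SE).

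For H = 60:

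- 60 v 90: SE = √(1/60 + 1/90) = 0.1667
- 30 v 90: SE = √(1/30 + 1/90) = 0.2108

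| b (SD) | Bias (SD) | bias/SE, 60 v 90 | Type I error: normal / simulated t | bias/SE, 30 v 90 | Type I error: normal / simulated t |
|---|---|---|---|---|---|
| 0.1 | 0.067 | 0.40 | 6.9 / 6.8% | 0.32 | 6.2 / 6.1% |
| 0.2 | 0.133 | 0.80 | 12.6 / 12.4% | 0.63 | 9.7 / 9.6% |
| 0.3 | 0.200 | 1.20 | 22.4 / 21.9% | 0.95 | 15.8 / 15.3% |

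The t column comes from 200,000 simulated pooled-variance t-tests per cell. It runs slightly lower because shifted past patients also inflate the control-side variance.

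*Opposite direction* (60 v 30 + H, true benefit 0.5 SD, normal approximation):

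- Randomised controls only: Φ(0.5/0.2236 − 1.96) = 61%
- 60 unshifted past patients: Φ(0.5/0.1667 − 1.96) = 85%
- The same 60 if 0.3 SD longer: Φ((0.5 − 0.2)/0.1667 − 1.96) = 44%

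The t-test gives 60, 85 and 43%.

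**Precision given up by using randomised controls only** (ratio of SEs):

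| H | 60 v 30: SE 0.2236 against | Wider by | 30 v 30: SE 0.2582 against | Wider by |
|---|---|---|---|---|
| 30 | 0.1826 | 22% | 0.2236 | 15% |
| 60 | 0.1667 | 34% | 0.2108 | 22% |
| 120 | 0.1528 | 46% | 0.2000 | 29% |

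**The case against.** The best case for the plan is that the comparator is already concurrent. The Study Summary, 3.4 and 3.5 describe an untreated randomised arm of 30, and no procedure for selecting past patients exists. Grammatically, the review of records can be a second activity beside the comparison. This stands as evidence against assuming that pooling is planned. It does not exclude pooling, and the stated aim of raising power still points to inferential use.

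A second objection is that 5.2 compares men of the same baseline stretched length and normalises the data, whereas the illustration uses an unadjusted test. That also stands in part. If past records held a comparable baseline, adjustment would remove the part of the shift due to baseline length. It would not remove a shift from era, measurement or selection, and the documents do not show that such records hold a comparable length.

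A reader might infer that the sponsor intends to pool external controls, or that this trial's type I error is 12% or 22%. The documents support neither. Pooling is one of two open readings, and every input to those rates except the arm size is assumed.

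**Conclusion.** The point holds as an unresolved specification in the primary comparison. The omission is certain: the historical records are undefined, and nothing reserves the primary contrast for randomised patients. The consequence depends on the meaning. If external patients are pooled, the bias is b × H/(30 + H) SD and the error rates above show its scale, conditional on the assumed H, b, unadjusted pooling, equal SDs, two-sided 5% and layout. The precision gain is then valid only with zero shift, which nothing in the plan allows to be checked. If participants' own charts are meant, no such bias arises and only the variable needs naming.

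The mismatch between pre-operative normalisation and post-operative stratification is a separate defect that holds under either reading. This should be fixed before results are seen. The severity rests on the missing specification, not on the illustrative rates.

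**What to change.** 1. State in 5.2 that the primary between-group comparison of penile length uses only the concurrently randomised arms, adjusted for stretched length measured after catheter removal.
2. Replace the pre-operative length in the normalisation sentence of 5.2 with that same post-catheter-removal baseline.
3. Say what the historical records are. If they are external patients, confine them to a labelled supportive analysis whose source, eligibility, measurement and method of combining are fixed before results are seen. If they are participants' own charts, say so and name the variable.

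The new primary statement must also name the visit and say whether the traction arms are combined; those choices are outside this point.

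**Cost.** Wording only, since the post-operative baseline is already collected and defines the strata. If external pooling was intended, its nominal precision gain leaves the primary analysis: for H = 30, 60 or 120 the interval is 22, 34 or 46% wider (60 v 30 + H), or 15, 22 or 29% wider (30 v 30 + H). Baseline adjustment is not offered as an offset, because applied equally to both analyses it leaves those ratios unchanged. If own charts were intended, a chart covariate stays usable once named. Moving the whole trial to a pre-operative baseline is not proposed; it would need chart extraction and restratification, which is more than wording.
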